5.2 Data Handling Conventions

5.2.1 Premature Withdrawal

The investigator may have discontinued a subject's study participation at any time during the study when the subject met the study termination criteria. In addition, a subject may have discontinued his or her participation without giving a reason at any time during the study. Should a subject's participation have been discontinued, the primary criterion for termination was recorded. Discontinued or withdrawn subjects were not replaced after enrollment. All available data from subjects who were withdrawn from the study were listed and all available planned data were included in summary.

5.2.2 Handling of Missing Data

With the exception of missing or partial dates (Section 5.2.3), no imputed values were used for missing data.

5.2.3 Handling of Missing/Partial Date

Completely missing start or end dates remained missing, with no imputation applied.

Partial dates were imputed using the below conventions:

- If the partial date was a start date and:
 - If only missing day, then impute as the first day of the month.
 - If missing both month and day then, impute as the first day of the year.
- If the partial date was an end date and:
 - If only missing day, then impute as the last day of the month.
 - If missing both month and day, impute as the last day of the year.

- If the partial date was in the same month (only missing day) or same year (missing both month and day) as the study treatment, and the imputed start date of an adverse event (not pretreatment event) was prior to the start of study treatment, then the start date of study treatment was assumed to be the start date. The AE would then be considered as start on treatment (worst case scenario).
- If the imputed end date was after the subject’s last visit date (or last contact date), then the last visit date (or last contact date), was considered as the end date.

The recorded partial date was displayed in the listings.

5.2.4 Definition of Baseline and Change from Baseline

Baseline was defined as the last non-missing measurement prior to or on the date of the first dose of study drug (Study Day 1).

The change from baseline was calculated by subtracting the baseline values from the individual post-baseline values. If either the baseline or post-baseline value was missing, the change from baseline was set to missing as well.

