## 9.3.5 Unscheduled Visit

An unscheduled visit may occur when the subject returns to the clinic at any time during the Treatment Period of the study for the evaluation of symptoms or side effects.

At minimum, the following procedures are to be completed with additional procedures at the investigator's discretion:

- Physical examination.
- GERD symptoms investigator assessment.
- Vital signs.
- Weight.
- AE assessment.
- Fasting gastrin.
- Concomitant medication(s).

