All subjects returned to the investigative site on Day -1, which was deemed as the Baseline. Subjects who had completed all of the Screening procedures and met all eligibility requirements and none of the exclusion criteria had routine fasting laboratory evaluations including fasting serum gastrin, a urine pregnancy test (all women subjects of childbearing potential), a physical examination and vital signs measurements to assure continued eligibility. In addition, subjects were assessed by the investigator for GERD symptoms such as heartburn, acid regurgitation, dysphagia, belching, and epigastric pain.

Subjects were dispensed study drug on Day -1 according to an Interactive Web Response System (IWRS) and began taking study drug on the following day (Day 1). Rescue medication continued to be supplied during the Treatment Period.

Subjects were randomized in a 1:1 ratio to one of the following 2 treatment groups during the 4-week Treatment Period:

Group I: dexlansoprazole capsules (30 mg QD)

[figure not shown]
Group II: placebo (QD)

During this 4-week Treatment Period, study drug was self-administered, orally, once a day, in the morning, without regard to food. Subjects continued to document the presence and maximum

severity of daytime and nighttime heartburn symptoms and record usage of rescue medication using an eDiary. Subject visits were conducted at Weeks 2 and 4 of the Treatment Period to collect and/or dispense study drug, assess GERD symptoms, review concomitant medication use, assess adverse events, and perform a physical examination including vital signs. In addition, at the Week 4/ Final Visit, all subjects underwent laboratory evaluations, ECG, fasting serum gastrin and urine pregnancy test (all women of childbearing potential). Subjects who prematurely discontinued after randomization underwent Week 4/Final Visit procedures no later than 5 days after the last dose of study drug.

A schematic of the study design is included as [Figure 2.a](#).

Figure 2.a Schematic of Study Design

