5.2.5 Definition of Study Days and Visit Window

Study day was calculated relative to the date of the first dose of study drug in the study. The study day prior to the first dose of study drug was calculated as:

$$\text{Date of assessment/event} - \text{date of first dose of study drug}$$

The study day on or after the first dose of study drug was calculated as:

$$\text{Date of assessment/event} - \text{date of first dose of study drug} + 1.$$

The visit windows for the post baseline visits were defined in [Table 5.a](#). If a subject had more than 1 measurement in the same visit window, the measurement closest to the scheduled visit was used. If 2 measurements in the same window were of equal distance to the scheduled visit, the measurement that occurred after the scheduled visit was used. If 2 or more measurements occurred on the same day, the last value obtained was used.

Table 5.a Visit Window

Visit	Scheduled Day	Safety Labs & Serum Gastrin	Vital Signs	ECG	GERD Symptoms Investigator Assessment
Baseline	Day -1	≤1	≤1	≤1	≤1
Week 2	Day 14	2-21	2-21	NA	2-21
Week 4	Day 28	22-35	22-35	2-35	22-35

Note: Safety labs (including gastrin), vital signs, and ECG data obtained more than 7 days after the last day of study drug and efficacy data obtained more than 7 days after the last day of study drug weren’t included in the analyses.

Diary entries were assigned to study days according to the beginning of the recall period. Specifically, entries completed in the evening (reporting heartburn during the day) were assigned

to the same day; entries completed in the morning (reporting heartburn during the night) were assigned to the previous day.

For the purpose of diary compliance calculation and derivation of diary-based endpoints, the last day of study drug wasn't included since the subject was not expected to have completed the diary entries for that day by the Week 4/Final Visit. Therefore, summaries for the 4 weeks of treatment included Study Day 1 through Study Day 35 or the day before the last dose of study drug, whichever occurred first.

For efficacy variables summarized by visit, the value closest to the last day of study drug was summarized for each subject, including those within 7 days of the last day of study drug. If 2 measurements were of equal distance to the last day of study drug, the later measurement was used.

AEs that started more than 30 days after the last dose of study drug were listed, but excluded from the summaries and analyses.

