5.3 Analysis Sets

All efficacy analyses were performed on the full analysis set (FAS), which was defined as all randomized subjects who receive at least 1 dose of study drug and had post-baseline (post Day -1) data for the appropriate efficacy variable. The safety analysis set included all randomized subjects who received at least one dose of study drug.

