5.13.1 Adverse Events

All AEs were coded using the Medical Dictionary for Regulatory Activities (MedDRA).

A treatment-emergent adverse event (TEAE) was defined as an AE that started or worsened on or after Study Day 1 (defined as day first dosed), and no more than 30 days after the last dose of study drug. All TEAEs were listed by subject number and MedDRA coding. A listing of all unique coded terms was also provided.

The number and percentage of subjects with treatment-emergent AEs was summarized in several different tables:

- All AEs by system organ class (SOC), high level term (HLT), and preferred term (PT).
- Treatment-related AEs by SOC, HLT, and PT.
- Most frequent AEs by SOC and PT (sorted by total frequency of PT occurring in $\geq 5\%$ of subjects in any treatment group).
- Most frequent treatment-related AEs (TRAEs) by HLT and PT (sorted by total frequency of HLT occurring in $\geq 2\%$ of subjects in any treatment group). If no events met the 2% criteria, the most frequent TRAEs were defined as those events occurring in 2 or more subjects.
- Severity of all AEs by SOC and PT (mild, moderate, or severe).
- Severity of TRAEs by SOC and PT (mild, moderate, or severe).
- Relationship to study drug for all AEs by SOC and PT (not related, related).

A subject with 2 or more AEs within the same level of the MedDRA term was counted only once in that level using the most extreme incident (most severe for the severity tables and related for the relationship to study drug tables).

Additionally, treatment-emergent serious adverse events, deaths, and TEAEs resulting in premature discontinuation from study drug were listed and summarized by SOC, HLT and PT. The most frequent treatment-emergent non-serious AEs were also summarized by SOC, HLT and PT.

A pretreatment event was defined as an AE that ends prior to Study Day 1 (defined as day first dosed), or ends but not worsens on or after Study Day 1 (defined as day first dosed). A list of

pretreatment AEs by subject number and MedDRA coding was presented separately. Pretreatment AEs were summarized by SOC and PT.

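### SAP 5.2.4 accepts a value from the first-dose date as baseline without requiring that it precede the dose, so a Day 1 unscheduled-visit value can displace the Day -1 safety baseline

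*SAP*

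**What the plan says.** - **Baseline rule.** SAP 5.2.4 takes the "last non-missing measurement prior to or on the date of the first dose of study drug". The test is the date of the first dose, not its time.
- **Window.** The baseline row of SAP Table 5.a reads "Baseline Day -1 ≤1 ≤1 ≤1 ≤1": scheduled at Day -1, with Study Day 1 or earlier accepted for laboratory tests and gastrin, vital signs, ECG and the investigator's GERD assessment. The earliest post-baseline window opens on Day 2.
- **Selection within a window.** SAP 5.2.5 adds: "If a subject had more than 1 measurement in the same visit window, the measurement closest to the scheduled visit was used". Ties go to the later value.
- **Day -1 as Baseline.** SAP 2.0 states: "All subjects returned to the investigative site on Day -1, which was deemed as the Baseline". Protocol 6.1 says the same and starts dosing the next day. Protocol 9.1.3 describes the baseline physical examination as a pretreatment assessment.
- **Post-baseline.** SAP 5.3 requires, for the FAS, "post-baseline (post Day -1) data for the appropriate efficacy variable".
- **Adverse events.** SAP 5.13.1 defines a treatment-emergent event as "an AE that started or worsened on or after Study Day 1".
- **Day 1 procedures.** Protocol 9.3.3.1 and Appendix A list only the start of study drug and the eDiary. Protocol 9.3.5 allows an unscheduled visit "at any time during the Treatment Period of the study for the evaluation of symptoms or side effects"; its minimum content includes vital signs, fasting gastrin and a GERD assessment. An ECG and other laboratory tests are at the investigator's discretion.

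**The concern.** A baseline should describe the subject before exposure. Here the Day 1 allowance serves no scheduled assessment, and the one Day 1 clinic visit the protocol provides for is prompted by symptoms or side effects. If the subject attends because of something felt after the first capsule, the reading taken then can become the reference for every later change. A return to normal would then look like a treatment-period fall, while the corresponding adverse event would still be counted as treatment-emergent. Day 1 would be pre-treatment in the measurement tables and on-treatment in the adverse-event tables for the same subject.

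**Working it through.** The documents give no figure to reproduce. The check applies their rules to a subject with a Day -1 value and a Day 1 value.

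**1. Study day (formulas in SAP 5.2.5).** Before the first dose: assessment date minus first-dose date. On or after it: the same difference plus 1.

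| Assessment | Date difference | Study Day | Window in Table 5.a |
|---|---|---|---|
| Day before first dose (Visit 2) | -1 | -1 | Baseline |
| Date of first dose (unscheduled visit) | 0 | 0 + 1 = 1 | Baseline |
| Next day | 1 | 1 + 1 = 2 | Week 2 (2-21); for ECG, Week 4 (2-35) |

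A Day 1 value falls in no post-baseline window.

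**2. Which value is baseline when both exist?**
- SAP 5.2.4, last non-missing: the Day 1 value.
- SAP 5.2.5, closest to the scheduled Day -1: distances are 0 and 1 calendar day, so the Day -1 value.

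The two rules give the same subject different baselines. SAP 5.2.5 introduces its windows as being for post-baseline visits, so it is unclear whether its selection rule reaches the baseline row at all.

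**3. ECG.** Appendix A schedules an ECG at Screening (Days -21 to -2) and Week 4, not on Day -1. In calendar days, a Day 1 ECG lies 1 day from Day -1. A Day -2 ECG also lies 1 day away, and the tie goes to the later value; any earlier screening ECG is further away. So a Day 1 ECG, if recorded, becomes baseline under both rules. (If distance is counted in study-day numbers, Day 1 is 2 from Day -1, and a Day -2 ECG would be kept under 5.2.5; a Day -3 ECG would tie and lose.)

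**4. Effect on one subject (illustrative pulse values; Appendix B limit above 120 bpm).** Day -1: 80. Day 1 after the dose: 125. Week 4: 82.
- Baseline under 5.2.4 is 125: change = 82 - 125 = -43.
- Baseline at Day -1 is 80: change = 82 - 80 = +2.

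**5. Effect on the QTc criterion.** Appendix C flags a value of at least 450 msec with a rise of at least 30 from baseline. If the Day 1 QTc is d msec above the pre-dose value, a Week 4 value must lie 30 + d above the pre-dose value to meet the change part. The Week 4 ECG interpretation is also cross-tabulated against baseline (SAP 5.13.4).

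**6. How many subjects?** The documents do not say. As an assumption only, 0% to 3% of the 215 treated subjects attending on Day 1 gives 0 to 6 (0.01 × 215 = 2.15; 0.03 × 215 = 6.45). Zero is as compatible with the documents as any other figure.

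**The case against.** Several points on the other side are sound.

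- **The closest-to-schedule rule may keep Day -1.** If it governs the baseline row, the pulse example gives +2, not -43. This stands for measurements taken on Day -1. It does not protect ECG, and it leaves 5.2.4 contradicted by the next section.
- **Post-dose timing is inferred.** No passage says that a Day 1 unscheduled visit follows the dose. Protocol 8.1.3.1 lets a missed dose be taken up to 12 hours late. For fasting blood, Protocol 7.4 has study drug held until after the draw, while Appendix A footnote (d) has it taken beforehand; those passages need reconciling, and until they are a Day 1 gastrin could fall on either side of the dose.
- **Day 1 can be a legitimate baseline date.** Study day is counted from the actual first dose and drug is dispensed at Visit 2. A subject who took the first capsule that same day has Visit 2 on Study Day 1. A blanket cut-off at Day -1 would discard a proper baseline.
- **The abnormal value need not vanish.** A reader might infer that a first-dose abnormality drops out of the markedly abnormal counts. The documents do not establish this: SAP 5.13.3 tabulates all individual vital signs meeting the criteria, with no stated window limit, and all vital-sign and ECG data are listed.
- **Efficacy is hardly touched.** The primary and secondary endpoints use diary days without this baseline. Investigator-assessed severity is a maximum over the preceding 7 days (Protocol 9.1.6), so a Day 1 assessment covers almost only pre-treatment days.

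**Conclusion.** The defect is real and limited. SAP 5.2.4 admits a first-dose-date value as baseline with no pre-dose condition, and it does not agree with the Day -1 Baseline visit, with post-baseline as used in SAP 5.3, with adverse events counted from Day 1 or, if that rule applies, with the selection rule in 5.2.5. A Day 1 unscheduled-visit value can therefore become the reference for vital signs and gastrin, and for ECG or other laboratory tests if done.

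Exposed are safety changes from baseline, the ECG shift table and QTc-change criterion and, slightly, the baseline-severity stratum of the CMH test in SAP 5.10.3. The number of affected subjects is unknown and may be zero.

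A reader might go further and infer that a first-dose reaction always becomes the subject's baseline, or that the trial's efficacy result is in doubt. Neither follows. The first needs a Day 1 visit, a measurement after the dose and 5.2.4 prevailing over 5.2.5 (for ECG, only the first two). The second fails because the primary and secondary endpoints do not use this baseline. The conclusion that a Day 1 value is probably post-dose rests on self-administered morning dosing.

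**What to change.** Use one rule in SAP 5.2.4, Table 5.a and 5.3:

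- Baseline is the scheduled Visit 2 (Day -1) value. If that is missing, or the test is not scheduled then (for example ECG), it is the last value before the first dose.
- A value on the first-dose date counts as baseline only if it comes from the scheduled Visit 2 or is documented as pre-dose. Put this condition on the Day 1 limit in Table 5.a rather than cutting the window at Day -1.
- All other Day 1 values are on-treatment and enter the on-treatment summaries of markedly abnormal values. In SAP 5.3, define post-baseline by the same rule.

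First count the Day 1 clinic records in the existing data. If there are none, only the wording changes; otherwise re-run the baseline flag and the dependent safety tables and GERD severity analysis. Opening the on-treatment period at Day 1 will not by itself bring the value into the by-visit changes, because the Week 2 reading nearest Day 14 is still selected; the markedly abnormal summary is where it would be seen.

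The cost is small. No passage requires the first-dose time to be recorded (Protocol 9.1.13 requires it for the ECG itself), so an untimed Day 1 make-up value would no longer serve as baseline.

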5.2.5 Definition of Study Days and Visit Window

Study day was calculated relative to the date of the first dose of study drug in the study. The study day prior to the first dose of study drug was calculated as:

$$\text{Date of assessment/event} - \text{date of first dose of study drug}$$

The study day on or after the first dose of study drug was calculated as:

$$\text{Date of assessment/event} - \text{date of first dose of study drug} + 1.$$

The visit windows for the post baseline visits were defined in [Table 5.a](#). If a subject had more than 1 measurement in the same visit window, the measurement closest to the scheduled visit was used. If 2 measurements in the same window were of equal distance to the scheduled visit, the measurement that occurred after the scheduled visit was used. If 2 or more measurements occurred on the same day, the last value obtained was used.

Table 5.a Visit Window

Visit	Scheduled Day	Safety Labs & Serum Gastrin	Vital Signs	ECG	GERD Symptoms Investigator Assessment
Baseline	Day -1	≤1	≤1	≤1	≤1
Week 2	Day 14	2-21	2-21	NA	2-21
Week 4	Day 28	22-35	22-35	2-35	22-35

Note: Safety labs (including gastrin), vital signs, and ECG data obtained more than 7 days after the last day of study drug and efficacy data obtained more than 7 days after the last day of study drug weren’t included in the analyses.

Diary entries were assigned to study days according to the beginning of the recall period. Specifically, entries completed in the evening (reporting heartburn during the day) were assigned

to the same day; entries completed in the morning (reporting heartburn during the night) were assigned to the previous day.

For the purpose of diary compliance calculation and derivation of diary-based endpoints, the last day of study drug wasn't included since the subject was not expected to have completed the diary entries for that day by the Week 4/Final Visit. Therefore, summaries for the 4 weeks of treatment included Study Day 1 through Study Day 35 or the day before the last dose of study drug, whichever occurred first.

For efficacy variables summarized by visit, the value closest to the last day of study drug was summarized for each subject, including those within 7 days of the last day of study drug. If 2 measurements were of equal distance to the last day of study drug, the later measurement was used.

AEs that started more than 30 days after the last dose of study drug were listed, but excluded from the summaries and analyses.

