## 7.1 Inclusion Criteria

Subject eligibility is determined according to the following criteria:

- 1. In the opinion of the investigator, the subject is capable of understanding and complying with protocol requirements.
- 2. The subject or, when applicable, the subject's legally acceptable representative signs and dates a written, informed consent form and any required privacy authorization prior to the initiation of any study procedures.
- 3. The subject is a man or woman and aged at least 18 years.
- 4. Subjects identifying their main symptom as a burning feeling in the mid epigastric area and/or chest area (ie, heartburn).
- 5. The subject must have a history of symptomatic GERD for 6 months or longer prior to Screening with GERD symptoms that were responsive to acid-suppressive therapy.
- 6. The subject must have episodes of heartburn for any 4 or more days during the 7 days prior to Day -1 as recorded in the eDiary.
- 7. All women subjects of child bearing potential who are sexually active agree to routinely use adequate contraception from signing of the informed consent throughout the duration of the study and for 30 days after the last dose of study medication.
- 8. All men subjects who are nonsterilized\* and sexually active with women partner of childbearing potential\* agree to use adequate contraception\* from signing of informed consent throughout the duration of the study and for 30 days after the last dose of study medication.

\*Definitions and acceptable methods of contraception are defined in Section 9.1.11 Contraception and Pregnancy Avoidance Procedure and reporting responsibilities are defined in Section 9.1.12 Pregnancy.

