# 9.1.6 GERD Symptoms Investigator Assessment

Subjects will have a GERD symptom assessment performed by the investigator during the Screening Period (on Day -1) and at the Week 4/Final Visits of the Treatment Period. The maximum severity of the GERD symptoms of heartburn, acid regurgitation, dysphagia, belching and epigastric pain will be assessed by appropriate site personnel as either none, mild, moderate, severe, or very severe as defined below, during the 7 days prior to the subject's study visit and recorded on the appropriate eCRF. The definitions for the symptoms being assessed are:

- Heartburn: A burning feeling in the mid epigastric area and/or chest area.
- Acid regurgitation: Flow of sour or bitter fluid into the mouth.
- Dysphagia: Difficulty in swallowing.
- Belching: The voiding of gas from the stomach through the mouth, which may be associated with acid regurgitation.
- Epigastric pain: Central upper abdominal pain.
- None: No symptoms.
- Mild: Symptom does not last long and is easily tolerated.
- Moderate: Symptom causes discomfort and/or interrupts usual activities (including sleep).
- Severe: Symptom causes great interference with usual activities and may be incapacitating (including sleep).

Dexlansoprazole Capsules	
Study No. TAK-390MR_302	Page 39 of 82
Protocol Incorporating Amendment No. 03	20 February 2017

• Very Severe: Symptom causes intense and constant discomfort and/or marked interference with usual activities (including sleep).

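### The Week 2 window for investigator symptom scores opens at Day 2, but each score looks back 7 days, so a score from Days 2-7 includes pre-dose symptoms; few subjects can be affected

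*SAP*

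**What the plan says.** SAP 5.2.5 states: "The visit windows for the post baseline visits were defined in" Table 5.a. In that table the Week 2 row reads "Week 2 Day 14 2-21 2-21 NA 2-21". The last entry belongs to the column "GERD Symptoms Investigator Assessment", so any such score from Day 2 to Day 21 counts as Week 2. The two entries before the ECG column give the same range for laboratory tests and vital signs.

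Protocol 9.1.6 defines what is scored: "The maximum severity of the GERD symptoms of heartburn, acid regurgitation, dysphagia, belching and epigastric pain will be assessed", and the reference period is "during the 7 days prior to the subject's study visit".

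SAP 5.2.5 adds four rules that bear on this:

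- "Study day was calculated relative to the date of the first dose of study drug in the study". The formulas give Day 1 for the first dose and Day -1 for the day before, with no Day 0.
- When a window holds several measurements, the one nearest the scheduled day (Day 14) is used, and a tie goes to the one after it.
- For efficacy variables summarised by visit, the value nearest the last day of study drug is used.
- Efficacy data from more than 7 days after the last day of study drug are left out. No rule removes a score whose look-back reaches before Day 1.

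The planned Week 2 visit has a window of ±3 days (Protocol 9.3.3.2). Earlier scores can arise at early-termination visits, due within 5 days of the last dose (Protocol 6.1 and 9.3.4), and at unscheduled visits (Protocol 9.3.5). Both include the symptom assessment.

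**The concern.** The window suits a measurement that describes the visit day. The symptom score describes the preceding week. For a visit in the first 7 days, part of that week lies before the first dose, and because the score is a maximum, one bad pre-dose day is enough to set it.

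Two features of the plan sharpen this. Entry requires recent heartburn: "The subject must have episodes of heartburn for any 4 or more days during the 7 days prior to Day -1". And the Week 2 analysis is a CMH test with baseline severity as the stratum (SAP 5.10.3), so an early score shares recall days with the variable it is stratified on.

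The same SAP section assigns diary entries by the start of their recall period, so the issue was recognised there but not carried over to this column. What is at stake is whether every Week 2 severity value is an on-treatment value. SAP 9.1 reports p=0.009 for heartburn at Week 2.

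**Working it through.** The plan states no figure for this, so the check is a calendar count.

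**Step 1: pre-dose days in the recall.** A visit on Day D recalls the 7 days before it. With no Day 0, the number before the first dose is max(0, 8 − D).

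**Step 2: overlap with the entry window.** The 7 days before Day -1 are Days -8 to -2, as SAP 5.6 confirms. The baseline score on Day -1 recalls the same days. For D from 2 to 7, the overlap is k = 7 − D days, since Day -1 falls outside it.

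**Step 3: chance of recalling a qualifying heartburn day.** Assume exactly 4 heartburn days placed at random in the 7 entry days. The chance that at least one lies in the k overlapping days is 1 − C(3,k)/C(7,k), with C(3,k) = 0 for k above 3.

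| Visit day | Recall (Days) | Pre-dose days | k | Chance |
|---|---|---|---|---|
| 2 | -6 to 1 | 6 | 5 | 100% |
| 3 | -5 to 2 | 5 | 4 | 100% |
| 4 | -4 to 3 | 4 | 3 | 34/35 = 97% |
| 5 | -3 to 4 | 3 | 2 | 18/21 = 86% |
| 6 | -2 to 5 | 2 | 1 | 4/7 = 57% |
| 7 | -1 to 6 | 1 | 0 | 0 from the entry days; Day -1 only |
| 8 | 1 to 7 | 0 | 0 | none |

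More than 4 heartburn days would raise the chances for Days 4-6.

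**Step 4: a worked record.** A subject has no symptoms from Day 1, stops, and is seen on Day 3. Of the entry days, only Days -8, -7 and -6 lie outside the recall. They can hold at most 3 of the 4 or more heartburn days, so at least one falls on Days -5 to -2. If the investigator applies the recall as defined, the Week 2 heartburn score is at least mild although on-treatment severity was none.

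**Step 5: when such a score is used.** A score on Days 2-7 is 12 to 7 days from Day 14; a score on Days 8-21 is at most 7 days from it. Of the 6 × 14 = 84 possible pairs, the earlier score wins none. The only tie, Day 7 against Day 21, goes to Day 21. An early score therefore stands only if Days 8-21 hold no score.

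**Step 6: how many subjects.** SAP 6.1 gives 205 subjects who completed all planned visits and 10 who discontinued study drug. If the completers' Week 2 visits fell on Days 8-21, at most 10 of 215 = 4.7% can be affected. Under the rule that favours the value nearest the last day of study drug, a discontinued subject's early score could be chosen over a later one, but within the same 10.

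**Step 7: Week 4.** That window opens at Day 22, which recalls Days 15-21, so it is unaffected.

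**The case against.** The strongest reply is that the closest-to-Day-14 rule already removes nearly all of the problem. That stands. A reader might infer that any unscheduled visit in the first week contaminates Week 2; it does not if the subject also has a score on Days 8-21. Subjects who stop in the first week can also be seen up to 5 days after the last dose, so some will be assessed on Day 8 or later.

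A reader might also take the discontinuations (6 on placebo, 4 on dexlansoprazole) as evidence of bias between arms. The documents do not support that. The counts cover the whole treatment period, differ by two subjects, and do not show who had a Day 2-7 score.

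The worked record is a favourable case. Where symptoms continue at similar severity after dosing, the pre-dose days do not change the maximum. The entry criterion concerns heartburn only, so the chances above say nothing about the other four symptoms.

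Finally, contiguous windows keep early-termination data in the analysis. That is a legitimate aim, but here what is kept is partly a baseline value.

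**Conclusion.** The mismatch between the window and the recall period is real and exact for Days 2-7. Adding pre-dose days can only raise a subject's score or leave it as it is, compared with the on-treatment days in the same recall. How that falls between the arms is unknown.

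The size is minor: at most about 10 of 215 subjects, possibly none, in the Week 2 tests of an additional endpoint. It would be tempting to conclude that the reported Week 2 heartburn result is unsafe. Nothing in the documents shows that; stop dates are not given in the text, and the effect is likely small.

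This rests on two assumptions: that the visit day is not part of the 7 days, as the wording implies (if it were, Days 2-6 would be affected), and that completers had a Week 2 score on Days 8-21.

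**What to change.** In Table 5.a, change the Week 2 entry for the investigator symptom assessment to Days 8-21, and list scores from Days 2-7 without counting them as Week 2. Day 8 is the first visit day whose whole recall follows the first dose, and the planned visit (Day 14 ± 3, so Days 11-17) is untouched.

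The document already reports unblinded results, so for this trial the step is to state how many Day 2-7 scores were used as Week 2 values, by arm, and to rerun the Week 2 CMH tests without them as a sensitivity analysis, labelled post hoc.

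The cost is one table cell and one rerun. The downside is that a few early stoppers will have no Week 2 value, since SAP 5.2.2 allows no imputation here.

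Scoring early visits as the maximum since the first dose is not a good substitute. It gives early stoppers a look-back of 1 to 6 days against 7 for everyone else, a maximum over fewer days tends to be lower, and it alters the assessment defined in Protocol 9.1.6.
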